# Statistical Analysis Plan

Study alias & e-track number(s): Flu CC-SUIV-AS03-001 (201598)

- Geometric mean titer (GMT) at Day 0, 42, *and final timepoint (for persistence) (i.e., Day 182 for the Q-Pan-H1N1-019, Q-PAN-H9N2-001 and Day 385 for the CC-Pan-H5N1 and Q-Pan H5N1-AS03-21 study cohorts)*
- Percentage of subjects with a  $\geq 4$ -fold rise from Day 0 to Day 42
- Mean geometric increase (MGI) at Day 42 *and final timepoint (for persistence) compared to Day 0 (i.e., Day 182 for the Q-Pan-H1N1-019, Q-PAN-H9N2-001 and Day 385 for the CC-Pan-H5N1 and Q-Pan H5N1-AS03-21 study cohorts)*
- *For adult subject samples from the Q-Pan-005 study cohort:*
  - *Seropositive rate at Day 0, 42, 549, 591, and 729 for group C and Day 182, 224, 549, 591, and 729 for group G*
  - *Geometric mean titer (GMT) at Day 0, 42, 549, 591, and 729 for group C and Day 182, 224, 549, 591, and 729 for group G*
  - *Percentage of subjects with a  $\geq 4$ -fold rise*
    - *For group C: From Day 0 to Day 42, from Day 549 to Day 591 and from Day 0 to Day 591*
    - *For group G: From Day 182 to Day 224, from Day 549 to Day 591 and from Day 182 to Day 591*
  - *Mean geometric increase (MGI) at Day 42, 549, 591, and 729 compared to Day 0 for group C and Day 224, 549, 591, and 729 compared to Day 182 for group G*
- *For adult subject samples from the H5N1-012 study cohort (groups VT/VT/12M and VT/IN/12M):*
  - *Seropositivity rate at Day 0, 21, M12, M12+21days, and M18*
  - *GMT at Day 0, 21, M12, M12+21days, and M18*
  - *Percentage of subjects with a  $\geq 4$ -fold rise from Day 0 to Day 21, from M12 to M12+21days, and from Day 0 to M12+21days*
  - *MGI at Day 0, 21, M12, M12+21, and M18*
- *For adult subject samples from the FLUD-QIV-015 study cohort:*
  - *Seropositive rate at Day 0 and 21*
  - *Geometric mean titer (GMT) at Day 0 and 21*
  - *Percentage of subjects with a  $\geq 4$ -fold rise from Day 0 to Day 21*
  - *Mean geometric increase (MGI) at Day 21 compared to Day 0*

# Statistical Analysis Plan

Study alias & e-track number(s): Flu CC-SUIV-AS03-001 (201598)

4. Vaccine-heterosubtypic virus titer by microneutralization (MN) for *all* subjects who received an AS vaccine in the *listed study cohorts*. The following aggregate variables will be calculated with 95% CI:
- *For adult subject samples from the CC-Pan H5N1-001, Q-Pan H1N1-019, Q-Pan H9N2-001, and Q-Pan H5N1-AS03-21 study cohorts:*
    - Seropositive rate at Day 0 and Day 42
    - Geometric mean titer (GMT) at Day 0 and Day 42
    - Percentage of subjects with a  $\geq 4$ -fold rise from Day 0 to Day 42
    - Mean geometric increase (MGI) at Day 42 compared to Day 0
  - *For adult subject samples from the Q-Pan-005 study cohort:*
    - Seropositive rate at Day 0, Day 42, Day 549 and Day 591 for group C and Day 182, Day 224, Day 549 and Day 591 for group G
    - Geometric mean titer (GMT) at Day 0, Day 42, Day 549 and Day 591 for group C and Day 182, Day 224, Day 549 and Day 591 for group G
    - Percentage of subjects with a  $\geq 4$ -fold rise
      - For group C: From Day 0 to Day 42, from Day 549 to Day 591 and from Day 0 to Day 591
      - For group G: From Day 182 to Day 224, from Day 549 to Day 591 and from Day 182 to Day 591
    - Mean geometric increase (MGI) at Day 42, 549, and 591 compared to Day 0 for group C and Day 224, 549, and 591 compared to Day 182 for group G
  - *For adult subject samples from the H5N1-012 study cohort (groups VT/VT/12M and VT/IN/12M):*
    - Seropositivity rate at Day 0, 21, M1, and M12+21 days
    - GMT at Day 0, 21, M12, and M12+21 days
    - Percentage of subjects with a  $\geq 4$ -fold rise from Day 0 to Day 21, from M12 to M12+21 days, and from Day 0 to M12+21 days
    - MGI at Day 0, 21, M12, and M12+21
  - *For adult subject samples from the FLU D-QIV-015 study cohort:*
    - Seropositive rate at Day 0 and 21
    - Geometric mean titer (GMT) at Day 0 and 21
    - Percentage of subjects with a  $\geq 4$ -fold rise from Day 0 to Day 21
    - Mean geometric increase (MGI) at Day 21 compared to Day 0

# Statistical Analysis Plan

Study alias & e-track number(s): Flu CC-SUIV-AS03-001 (201598)

## 4.2. Secondary endpoints

*With respect to samples from the HA Group 1-related studies (i.e., with H1N1, H5N1, and H9N2 pandemic, and IIV4 seasonal, influenza vaccines):*

1. Levels of anti-H1 stalk antibody by ELISA for all the subjects in the adult **CC-Pan H5N1-001, the Q-Pan H1N1-019 and the Q-Pan H9N2-001** study cohort. The following aggregate variables will be calculated with 95% CI to assess the effect of adjuvant relative to non-adjuvant in each study cohort at D21, D42, and 182 (and at Day 385 for the **CC-Pan-H5N1** study cohort only)
  - Geometric mean titer ratio (AS Group/no AS group **within each study**)
  - Difference (AS group minus no AS group **within each study**) of percentage in subjects with a  $\geq 4$ -fold rise from Day 0
2. Levels of HI antibody to pandemic vaccine homologous virus at Day 0 in all subjects **in all study cohorts (but Day 182 for group G of Q-Pan-005 study cohort)** by treatment group and level of HI antibody to A/California/7/09 (or a like virus) **in subjects from the CC-Pan-H5N1-001, Q-Pan-H9N2-001 and Q-PAN-005 and H5N1-012 study cohorts (Day 182 for group G of Q-Pan-005 and Day 0 for the other subjects)**. The following aggregate variable will be calculated with 95% CI:
  - Seropositive rate at Day 0 **in all subjects except for group G of the Q-Pan-005 study**
  - **Seropositive rate at Day 182 for group G of the Q-Pan-005 study cohort**

## 4.3. Tertiary endpoints

*With respect to samples from the HA Group 1-related studies (i.e., with H1N1, H5N1, and H9N2 pandemic, and IIV4 seasonal, influenza vaccines):*

- **Levels of anti-N1 NA antibody by ELISA for subjects in the H1N1 study cohort.** The following aggregate variables will be calculated with 95% CI:
  - **Seropositive rate at Day 0, 21, 42, 182**
  - **Geometric mean titer (GMT) at Day 0, 21, 42, 182**
  - **Percentage of subjects with a  $\geq 4$ -fold rise from Day 0 to Day 21, Day 42 and Day 182**
  - **Mean geometric increase (MGI) at Day 21, 42, 182 compared to Day 0**
- **Levels of anti-N1 NA antibody by ELISA for subjects in the H1N1 study cohort with respect to treatment group.** The following aggregate variables will be

# Statistical Analysis Plan

Study alias & e-track number(s): Flu CC-SUIV-AS03-001 (201598)

*calculated with 95% CI to assess the effect of adjuvant relative to non-adjuvant at D21, D42, and 182*

- **Geometric mean titer ratio (AS Group/no AS group)**
- **Difference (AS group minus no AS group) of percentage in subjects with a  $\geq 4$ -fold rise from Day 0**
- Levels of vaccine homologous neutralizing antibody and levels of anti-H1 stalk antibody by microneutralization at Day 0 and 21 for the subjects who received an adjuvant system (AS) vaccine in both the adult and pediatric H5N1 and H9N2 study cohorts. The following aggregate variable will be calculated with 95% CI:
  - Correlation between the level of neutralizing antibody to the H1 stalk with the level of vaccine homologous neutralizing antibody at Day 0 and 21
- Vaccine-homologous virus HI titer at Day 0 and level of anti-H1 stalk antibody by ELISA at Day 0 and Day 21 in the adult H5N1, H9N2 and H1N1 study cohorts. The following aggregate variable will be calculated with 95% CI:
  - Mean geometric increase (MGI) for anti-H1 stalk ELISA at Day 21 compared to Day 0
- Cell Mediated Immunity (CMI) parameters at Day 0, 7, 21, and 28 will be evaluated for subjects in the H9N2 study cohort in terms of frequencies of:
  - Antigen-specific CD4+/CD8+ T Cells identified as CD4/CD8 T-cells producing two or more markers within CD40L, IL-2, TNF- $\alpha$ , IFN- $\gamma$  upon in vitro stimulation using A/chicken/Hong Kong/G9/1997 (H9N2) split virus, A/California (H1N1) split virus or A/ Uruguay/716/2007 (H3N2) split virus
  - B memory cells reactive with the following antigens: A/chicken/Hong Kong/G9/1997 (H9N2) split virus ,H1 stalk domain presented as a recombinant protein chimeric HA 6/1, H9 globular HA domain presented as a recombinant protein, N2 presented as a recombinant protein if available
  - Plasmablasts reactive with the following antigens: A/chicken/Hong Kong/G9/1997 (H9N2) split virus ,H1 stalk domain presented as a recombinant protein chimeric HA 6/1, H9 globular HA domain presented as a recombinant protein, N2 presented as a recombinant protein if available
- Levels of anti-N2 NA antibody, levels of anti-H9 HA head domain antibody, and levels of anti-full length H9 HA by ELISA (A/chicken/Hong Kong/G9/1997) at Day 0, 21, and 42 for subjects in the H9N2 study cohort. The following aggregate variable will be calculated with 95% CI:
  - Seropositive rate at Day 0, 21, and 42
  - Geometric mean titer (GMT) at Day 0, 21, and 42

# Statistical Analysis Plan

Study alias & e-track number(s): Flu CC-SUIV-AS03-001 (201598)

- Percentage of subjects with a  $\geq 4$ -fold rise from Day 0 to Day 21, and Day 42
- Mean geometric increase (MGI) at Day 21 and 42 compared to Day 0

*With respect to samples from the HA Group 2-related study (i.e., from adult subjects who received H7N9 vaccine)*

1. *Levels of anti-H3 stalk antibody by ELISA for all subjects. The following aggregate variables will be calculated with 95% CI for each treatment group:*
  - *Seropositive rate at Day 0, 21, 42, Month 6, and Month 12*
  - *Geometric mean titer (GMT) at Day 0, 21, 42, Month 6, and Month 12*
  - *Percentage of subjects with a  $\geq 4$ -fold rise from Day 0 to Day 21 and from Day 0 to Day 42*
  - *Percentage of subjects with a  $\geq 10$ -fold rise from Day 0 to Day 21 and from Day 0 to Day 42*
  - *Mean geometric increase (MGI) at Day 21, 42, Month 6, and Month 12 compared to Day 0*
2. *Levels of anti-H3 stalk antibody by microneutralization (MN) for the subjects who received an adjuvant system (AS) vaccine. The following aggregate variables will be calculated with 95% CI:*
  - *Seropositive rate at Day 0, 21, 42, Month 6, and Month 12*
  - *Geometric mean titer (GMT) at Day 0, 21, 42, Month 6, and Month 12*
  - *Percentage of subjects with a  $\geq 4$ -fold rise from Day 0 to Day 21 and from Day 0 to Day 42*
  - *Percentage of subjects with a  $\geq 10$ -fold rise from Day 0 to Day 21 and from Day 0 to Day 42*
  - *Mean geometric increase (MGI) at Day 21, 42, Month 6, and Month 12 compared to Day 0*
3. *Levels of anti-H4 and anti-H10 antibody by ELISA for all subjects who received an AS vaccine. The following aggregate variables will be calculated with 95% CI:*
  - *Seropositive rate at Day 0, 42, and Month 12 (for persistency)*
  - *Geometric mean titer (GMT) at Day 0, 42, and Month 12*
  - *Percentage of subjects with a  $\geq 4$ -fold rise from Day 0 to Day 42 and from Day 0 to Month 12*
  - *Percentage of subjects with a  $\geq 10$ -fold rise from Day 0 to Day 42 and from Day 0 to Month 12*

# Statistical Analysis Plan

Study alias & e-track number(s): Flu CC-SUIV-AS03-001 (201598)

- *Mean geometric increase (MGI) at Day 42 and at Month 12 compared to Day 0*
4. *Vaccine-heterosubtypic virus titer by microneutralization (MN) for all subjects who received an AS vaccine in each study cohort. The following aggregate variables will be calculated with 95% CI:*
- *Seropositive rate at Day 0 and Day 42*
  - *Geometric mean titer (GMT) at Day 0 and Day 42*
  - *Percentage of subjects with a  $\geq 4$ -fold rise from Day 0 to Day 42*
  - *Percentage of subjects with a  $\geq 10$ -fold rise from Day 0 to Day 42*
  - *Mean geometric increase (MGI) at Day 42 compared to Day 0*
5. *Levels of anti-H3 stalk antibody by ELISA for all subjects. The following aggregate variables will be calculated with 95% CI to assess the effect of adjuvant relative to non-adjuvant at D21, D42, Month 6, and Month 12*
- *Geometric mean titer ratio (AS Group/no AS group)*
  - *Difference (AS group minus no AS group) of percentage in subjects with a  $\geq 4$ -fold rise from Day 0*

## 5. STUDY POPULATION

One cohort has been defined for analyses:

### 5.1.1. Total cohort

The total cohort (TC) for immunogenicity analysis will include all subjects from each study cohort with available results for this study. All analyses will be based on the total cohort. All the subjects selected are from the ATP cohort for immunogenicity of respective retrospective studies.

## 6. STATISTICAL METHODS

All analyses will be descriptive.

### 6.1. Analysis of demographics/baseline characteristics

Demographic characteristics (age at first study vaccination in years (months for the children 6-35 months of age), gender, ethnicity and geographical ancestry), and vaccination history, of each study cohort, summarized by treatment group in each study using descriptive statistics:

# Statistical Analysis Plan

Study alias & e-track number(s): Flu CC-SUIV-AS03-001 (201598)

- Mean, median, standard deviation will be provided for continuous data such as age.
- Percentage of subjects with baseline (D0) seropositivity by HI assay to the pandemic vaccine homologous virus for all subjects
- Percentage of subjects with baseline (D0) seropositivity by HI assay to A/California/7/09 (or a like virus) in the **CC-Pan-H5N1-001** and **Q-Pan-H9N2-001** study cohort (if data become available)

## 6.2. Analysis of immunogenicity

### 6.2.1. Within groups assessment

For each study group in the each **HA Group 1-related** study cohort (at each time point at which the tests are done and results are available) by anti-H1 stalk ELISA for all subjects, anti-H1 stalk MN (for subjects who received an adjuvant system (AS) vaccine *and for subjects in the D-QIV-015 study cohort*), anti-H2 and anti-H18 full length HA by ELISA (for subjects who received an adjuvant system [AS] vaccine *and for subjects in the D-QIV-015 study cohort*), **vaccine heterosubtypic MN (for subjects who received an adjuvant system [AS] vaccine and for subjects in the D-QIV-015 study cohort)**, the following analyses will be performed:

- Seropositivity rates and GMTs for anti-H1 stalk ELISA, anti-H1 stalk MN, vaccine heterologous MN, anti-H2 full length HA ELISA, anti-H18 full length HA ELISA, and anti-N1 NA ELISA (for H1N1 cohort), with exact 95% CI, will be calculated.
- MGI with 95% CI will be tabulated for anti-H1 stalk ELISA, anti-H1 stalk MN, vaccine heterologous MN, anti-H2 full length HA ELISA, anti-H18 full length HA ELISA and anti-N1 NA ELISA (for H1N1 cohort).
- Percentage of subjects with at least 4-fold increase from Day 0 *to all applicable timepoints per endpoint (from Day 182 for Group G subjects in the Q-Pan-005 study cohort)* with exact 95% CI, will be calculated (*refer to endpoint*)
- *Percentage of subjects with at least 10-fold increase from Day 0 to all applicable timepoints per endpoint (from Day 182 for Group G subjects in the Q-Pan-005 study cohort)* with exact 95% CI, will be calculated (*refer to endpoint*)
- The distribution of antibody titers for anti-H1 stalk ELISA will be displayed using reverse cumulative distribution curves.
- For AS group, the scatter plot of neutralizing antibody results to the H1 stalk with the vaccine homologous neutralizing antibody results *at all timepoints* will be presented to examine the correlation in study cohort H9N2 and both adult and pediatric H5N1 study cohorts. One scatter plot will be developed for each study/product. Furthermore, the correlation between the level of neutralizing antibody to the H1 stalk with the level of vaccine homologous neutralizing antibody *at all vaccination*

# Statistical Analysis Plan

Study alias & e-track number(s): Flu CC-SUIV-AS03-001 (201598)

**timepoints** may be explored using a Deming regression if needed in study cohort H9N2 and both adult and pediatric H5N1 study cohorts. However, the results should be interpreted with caution due to small sample size and testing result variations in vaccine homologous MN and H1 stalk MN.

- the scatter plot of ELISA antibody results to the H1 stalk [recombinant trimeric cHA (cH6/1N5)] with the microneutralizing antibody results to the H1 stalk [chimeric virus (cH6/1N5)] **at all timepoints** will be presented to examine the correlation in all the study cohort. One scatter plot will be developed for each study/product. Furthermore, the correlation between the level of ELISA antibody with the level of microneutralizing antibody to the H1 stalk **at all vaccination timepoints** may be explored using a Deming regression. However, the results should be interpreted with caution due to small sample size and testing result variations in H1 stalk ELISA and H1 stalk MN.
- For seropositive subjects by HI assay to the vaccine homologous virus at D0, MGI at Day 21 compared to Day 0 by anti-H1 stalk ELISA (with 95% CI) will be tabulated in the adult H5N1, H9N2 and H1N1 study cohort.
- CMI summaries will be generated for the H9N2 cohort only. The frequency of the response for B-cell, plasma-cell and T-cell elicited by vaccine components measured in a sub-cohort of subjects at Days 0, 7, 21 and 28 will be described according to the technical specifications provided by R&D (Clinical Data – Information Sheet).
- For H9N2 study cohort only, SP, GMT, MGI, and percentage of subjects with  $\geq 4$ -fold rise from Day 0 to Day 21 and 42 by anti-N2 NA antibody, anti-H9 HA head domain antibody, and anti-full length H9 HA antibody (with exact 95%CI) will be calculated.

*For each study group in HA Group 2 -related study H7N9 cohort (at each time point at which the tests are done and results are available), anti-H3 stalk ELISA for all subjects, anti-H3 stalk MN, anti-H4 HA full length ELISA, anti-H10 HA full length ELISA and vaccine heterologous MN antibody levels (for subjects who received an adjuvant system [AS] vaccine), the following analyses will be performed:*

- Seropositivity rates and GMTs for anti-H3 stalk ELISA, anti-H3 stalk MN, anti-H4 full length HA ELISA, anti-H10 HA full length ELISA and vaccine heterologous MN, with exact 95% CI, will be calculated.*
- MGI with 95% CI will be tabulated for anti-H3 stalk ELISA, anti-H3 stalk MN, anti-H4 HA full length ELISA, anti-H10 HA full length ELISA and vaccine heterologous MN*
- Percentage of subjects with at least 4-fold increase from Day 0 to Day 42 for anti-H3 stalk ELISA, anti-H1 stalk MN, anti-H4 full length HA ELISA, anti-H10 full length HA ELISA and vaccine heterologous MN, with exact 95% CI, will be calculated.*

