## 1. DOCUMENT HISTORY

Date	Description	Protocol Version
30-JUN-2015	Version 1	Amendment 1 Final - 10-MAR-2015
20-JAN-2017	Amendment 1 Changes from the previous version:- 

1. Addition of new study cohorts and groups

2. Changes in the study design, objective, endpoints and analysis to be performed per Protocol amendment 2.

3. The ATP cohort for immunogenicity analysis has been removed.

4. The correlation analysis will be performed including all timepoints together

	Amendment 2 Final – 01-SEP-2016

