### 3.3. Tertiary objective

*With respect to samples from the HA Group 1-related studies (i.e., with H1N1, H5N1 and H9N2 pandemic, and IIV4 seasonal, influenza vaccines):*

- To describe the anti-N1 NA ELISA antibody levels at D0, D21, D42, and D182 for subjects **in the Q-PAN-H1N1-019 study cohort**, by treatment group
- To assess the effect of adjuvant in the **Q-PAN-H1N1-019** study cohort in terms of the adjusted anti-N1 NA ELISA GMT ratio (AS group/no AS group) at D21, D42, D182, and in terms of the difference in percentage of subjects (AS group minus no AS group) with a  $\geq 4$ -fold rise from Day 0 to Day 21 and D42, D182.
- To explore the correlation between the level of neutralizing antibody to the H1 stalk with the level of vaccine homologous neutralizing antibody, at Day 0 and 21 in the adult **Q-Pan-H9N2-001 and CC-Pan-H5N1-001 study cohorts and in the pediatric Q-Pan H5N1-AS03-021** study cohorts (AS group only)
- To explore the effect of being seropositive by HI test to the vaccine homologous virus at D0 on the MGI (D21/D0) of anti-H1 stalk ELISA antibody in the adult H5N1, H9N2 and H1N1 study cohorts
- To explore the cell mediated immune response to H9N2 vaccine with respect to T cells, B memory cells and plasmablasts reactive with H9N2 and related antigens at Days 0, 7, 21, and 28 in selected vaccine groups **of the Q-Pan-H9N2-001 study cohort**
- To further characterize the humoral immune response to H9N2 vaccine **in the Q-Pan-H9N2-001 study cohort** by ELISA using the purified recombinant viral proteins (H9 HA head domain, H9 full length, N2)

*With respect to samples from the HA group 2-related study cohort (H7N9 study) (adult subjects):*

- **To describe the anti-H3 stalk ELISA antibody levels:**
  - *At baseline Day 0 (D0), post-dose 1 at Day 21 (D21), post-dose 2 at Day 42 (D42), Month 6, and Month 12 by treatment group (unadjuvanted or adjuvanted vaccine), from the primary completed H7N9 study*
- **To describe the anti-H3 stalk microneutralization (MN) antibody levels (target virus: cH14/3Nx):**
  - *At baseline Day 0 (D0), post-dose 1 at Day 21 (D21), post-dose 2 at Day 42 (D42), Month 6, and Month 12 for subjects who received adjuvanted vaccine*

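### Section 6.2.1 pools all timepoints and offers only an optional Deming fit, so the Day 0 / Day 21 correlation with 95% CI set in 3.3 and 4.3 is never produced

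*SAP*

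**What the plan says.** Section 3.3 asks for the correlation of neutralizing antibody to the H1 stalk "with the level of vaccine homologous neutralizing antibody, at Day 0 and 21 in the adult" H9N2 and H5N1 cohorts and the pediatric H5N1 cohort, adjuvanted groups only. Section 4.3 carries this into an endpoint: "The following aggregate variable will be calculated with 95% CI", namely "Correlation between the level of neutralizing antibody to the H1 stalk with the level of vaccine homologous neutralizing antibody at Day 0 and 21".

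Section 6.2.1 does something else. It plans a scatter plot of the two MN results over all timepoints, with the rule "One scatter plot will be developed for each study/product". It adds that the correlation over all vaccination timepoints "may be explored using a Deming regression if needed in study cohort H9N2 and both adult and pediatric H5N1 study cohorts". Taken alone, that could mean each timepoint in turn. Item 4 of the Document History rules this out: "The correlation analysis will be performed including all timepoints together". The only warning in 6.2.1 is that "the results should be interpreted with caution due to small sample size and testing result variations in vaccine homologous MN and H1 stalk MN".

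Section 6.2.1 uses the same pooled plot and optional Deming regression for ELISA against MN, both for the H1 stalk and for the H3 stalk in the H7N9 cohort. No objective or endpoint sets timepoints for those two comparisons.

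**The concern.** There are two problems. First, the endpoint has no matching analysis: 6.2.1 names no correlation coefficient, no Day 0 or Day 21 estimate and no interval method, and its one named method does not estimate a correlation.

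Second, pooling changes what is estimated. The objective concerns whether subjects high on one assay are high on the other at a given time. Once pre- and post-dose samples share one plot, a rise on both assays spreads the points along a diagonal even if the assays are unrelated between subjects at each visit. A reader of the study report could take that pattern as agreement between stalk and homologous neutralization. The stated caution does not cover this, because more subjects or a more precise assay would not remove the effect.

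**Working it through.** The SAP gives no expected correlation, SD, rise or interval for this analysis, so there is no figure of its own to reproduce.

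**Step 1. Match endpoint to method.**

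| SAP section | Timepoints | Output |
|---|---|---|
| 3.3 | Day 0 and Day 21 | correlation |
| 4.3 | Day 0 and Day 21 | correlation with 95% CI |
| 6.2.1 | all, one plot per study | scatter plot; optional Deming slope and intercept |
| 7.1 | not applicable | CI methods for GMTs and proportions only |

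No row supplies the output promised in 4.3.

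**Step 2. Effect of a shared rise.** Take two equally sized timepoints, a rise of d (in within-timepoint SDs) on both assays, and correlation r_w within each timepoint. The timepoint means add d²/4 to each variance and to the covariance, so

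r_pooled = (r_w + d²/4) / (1 + d²/4).

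| d (SD) | d²/4 | r_pooled, r_w = 0 | r_pooled, r_w = 0.3 |
|---|---|---|---|
| 0.5 | 0.0625 | 0.06 | 0.34 |
| 1 | 0.25 | 0.20 | 0.44 |
| 1.5 | 0.5625 | 0.36 | 0.55 |
| 2 | 1 | 0.50 | 0.65 |
| 3 | 2.25 | 0.69 | 0.78 |

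In titer terms, with an assumed log10 SD of 0.5 and r_w = 0, a 4-fold rise (0.602 log10) gives 0.0906 / (0.25 + 0.0906) = 0.27. A 10-fold rise gives 0.25 / (0.25 + 0.25) = 0.50. If only one assay rises, the covariance term vanishes and no correlation is created.

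**Step 3. Interval width.** Section 2 gives about 30 subjects per adjuvanted group (Table 1: 20-30). For homologous MN, selection requires Day 0 and Day 21 in the adult H5N1 and H9N2 studies, and results at Day 0, 21, 42 or 385 in the children. The ratio of the true standard error of Fisher-z r to the naive one (every sample independent) was simulated with 30 subjects, r_w = 0 and 2000 runs per setting. The columns are the assumed within-subject correlation, equal in both assays.

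| Setting | 0.5 | 0.7 | 0.9 |
|---|---|---|---|
| 2 timepoints, no rise | 1.13 | 1.23 | 1.38 |
| 2 timepoints, 1 SD rise | 1.00 | 1.07 | 1.13 |
| 2 timepoints, 2 SD rise | 0.89 | 0.93 | 1.01 |
| 4 timepoints, no rise | 1.29 | 1.58 | 1.88 |
| 4 timepoints, means 0, 1, 1.5, 0.5 SD | 1.12 | 1.37 | 1.55 |

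In the last row, a nominal 95% interval covers the pooled value in 92%, 84% and 78% of runs. With two timepoints and a 2 SD rise, coverage is 97%, 96% and 94%. With no within-subject correlation the ratio is 0.85 to 1.01 in every setting, so the interval is not too narrow.

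Missing the intended target is the larger problem. At within-subject correlation 0.7 and two timepoints, the naive pooled interval contains the true within-timepoint value of 0 in 63% of runs after a 1 SD rise and in 0.5% after a 2 SD rise.

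**Step 4. Precision after separating timepoints.** The Fisher interval at r = 0 is ±tanh(1.96/√(n − 3)). For n = 30 this is ±0.36 (width 0.72), and for n = 20 it is ±0.44 (width 0.89). Counting pooled samples as independent would show width 0.51 for 30 × 2 = 60 and 0.36 for 30 × 4 = 120.

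**The case against.** The analysis is tertiary, all analyses are described as descriptive, the Deming step is conditional, and a caution is attached. No decision rule depends on the result. This stands, and it limits severity.

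For ELISA against MN the defence is stronger. For the H1 stalk both assays use the same cH6/1N5 construct, so zero within-timepoint correlation is a weak reference case. The reference list cites method-comparison and errors-in-both-axes work, for which a wide titer range is a defensible choice. No Day 0/21 endpoint exists for these comparisons, so the charge of an unmet endpoint applies only to stalk MN against homologous MN. Repeated samples still need handling: stalk MN is planned at six timepoints per subject in H5N1-012 and in Q-Pan-005 group C.

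A reader might infer more than the document supports:

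- That the reported interval will be too narrow. The SAP fixes no interval and does not say that samples are treated as independent. Step 3 shows that the direction and size depend on the number of timepoints, the rise and the within-subject correlation.
- That the children form a Day 0 cluster at half the cut-off. They were selected as HI-negative to H1N1pdm09, which does not establish their stalk MN level. Section 7.1 gives the half-cut-off rule for GMT and fold-rise calculations, not for plots or Deming fits.
- That these correlations drive assay choice or the next study. Section 2 ties the next study's design to the booster and seasonal-vaccine response descriptions. It mentions H3 stalk assay performance without naming the correlation.

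**Conclusion.** The mismatch is established from the current text of 3.3, 4.3 and 6.2.1: carried out as written, the plan does not yield the Day 0 and Day 21 correlations with 95% CI.

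The pooling problem is real but conditional on both assays rising. Its size (r of 0.20 to 0.69 for rises of 1 to 3 SD from a true value of zero) rests on assumed rises, two equal timepoints and no within-timepoint correlation.

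On the interval, the supportable statement is that no method is specified. One that ignores repeated sampling can be too narrow when titers correlate within subject and there are about four or more timepoints. With Day 0 and Day 21 alone it is slightly narrow or not narrow after a rise of 1 to 2 SD. It is more clearly narrow (ratio 1.13 to 1.38) only when there is no rise, which is also when pooling creates no false correlation. The two effects should therefore not be added together.

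Severity is moderate to low.

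**What to change.** In 6.2.1, for stalk MN against homologous MN, compute the correlation of log10 titers with a 95% CI separately at Day 0 and at Day 21, and name the coefficient and the interval method. Keep any all-timepoint figure as supplementary, with timepoint means removed and a subject-level interval such as a bootstrap that resamples subjects.

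For ELISA against MN (H1 and H3 stalk), mark timepoints on the plot, report per-timepoint correlations beside the pooled fit, and account for repeated samples in any interval.

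Rewriting 3.3 and 4.3 to match 6.2.1 would remove the contradiction, but it would leave the shared rise mixed into the estimate and still require an interval method.

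The cost is a few sentences of SAP text and little programming. The price is precision: about 0.72 wide at r = 0 with 30 subjects and 0.89 with 20. That is the information actually available at one timepoint.

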## 6.2.2. Between groups assessment

### 6.2.2.1. For adult H5N1, H9N2, and H1N1 study cohorts

- For each **Group 1-related** study and for anti-H1 stalk ELISA results for adult H5N1, H9N2 and H1N1 study cohort, if available:
  - The difference in percentage of subject with at least 4-fold increase at *all applicable timepoints (D21, D42, D182, and D385) for which data are available* compared to Day 0 (i.e. adjuvanted group minus non-adjuvanted group *within each study cohort*, and the asymptotic standardized 95% CI, will be computed for each study cohort, separately.
  - The adjusted GMT ratio (adjuvanted group to non-adjuvanted group *within each study cohort*) of anti-H1 stalk ELISA antibodies for adjuvanted vaccine over non-adjuvanted vaccine at all timepoints (D21, D42, D182, and D385) for which data are available and the two-sided 95% CI on each GMT ratio will be computed for each study cohort, separately. ANCOVA models on the logarithm10 transformation of the titers, including the vaccine group as fixed effect and age category (<30 years and >=30 years) and the anti-H1 stalk ELISA result at Day 0 as covariates.
- For H1N1 study cohort and for anti-N1 NA ELISA results, if available:
  - The difference in percentage of subject with at least 4-fold increase at all time points (D21, 42 and 182) compared to Day 0 (i.e. adjuvanted group minus non-adjuvanted group, and the asymptotic standardized 95% CI, will be computed.
  - The adjusted GMT ratio (adjuvanted group to non-adjuvanted group) of anti-N1 NA ELISA antibodies for adjuvanted vaccine over non-adjuvanted vaccine at all timepoints (D21, D42 and D182) for which data are available and the two-sided 95% CI on each GMT ratio will be computed. ANCOVA models on the logarithm10 transformation of the titers, including the vaccine group as fixed

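### The effect of baseline HI seropositivity on the stalk ELISA rise is a stated tertiary objective, but the SAP tabulates that rise only in seropositive subjects, so no planned output makes the comparison.

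*SAP*

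**What the plan says.** The objective, in SAP section 3.3, concerns the ELISA response and covers the adult H5N1, H9N2 and H1N1 cohorts: "To explore the effect of being seropositive by HI test to the vaccine homologous virus at D0 on the MGI (D21/D0) of anti-H1 stalk".

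The matching endpoint in section 4.3 lists the inputs as "Vaccine-homologous virus HI titer at Day 0 and level of anti-H1 stalk antibody by ELISA at Day 0 and Day 21", with no restriction to seropositive subjects. Its only summary variable is "Mean geometric increase (MGI) for anti-H1 stalk ELISA at Day 21 compared to Day 0". It names neither a split by serostatus nor a contrast.

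The analysis in section 6.2.1, a table of the stalk ELISA rise with a 95% CI, is limited to one stratum: "For seropositive subjects by HI assay to the vaccine homologous virus at D0, MGI at Day 21 compared to Day 0".

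Three other parts of the plan come near the question:

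- Section 6.2.1 also states "MGI with 95% CI will be tabulated for anti-H1 stalk ELISA, anti-H1 stalk MN, vaccine heterologous MN" and further assays, for each study group as a whole.
- Sections 4.2 and 6.1 give the proportion HI seropositive at baseline, but not the MGI by serostatus.
- The ANCOVA models in section 6.2.2.1 contain vaccine group, age category and "the anti-H1 stalk ELISA result at Day 0 as covariates". HI serostatus is not a term.

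**The concern.** An effect of serostatus is a comparison of subjects who have it with subjects who do not. The planned table shows one side. Whatever value it gives, a reader cannot tell whether seropositive subjects rose more, less or about as much as seronegative subjects.

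The SAP handles its other effects differently. For the effect of adjuvant, section 6.2.2.1 plans a GMT ratio and a difference in percentages, each with a 95% CI. For the effect of age in the H5N1-012 cohort, section 2 plans stratification into both age bands. Only the serostatus effect is given a single stratum, which looks like an omission rather than a choice.

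At stake is one exploratory statement, on whether prior homologous HI antibody goes with a larger or smaller stalk response. If the comparator is chosen only once results are in, that choice will be post hoc.

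**Working it through.** The SAP gives no sample size, power or precision figure for this objective, so there is no stated number to reproduce. The check is whether the planned outputs identify the effect.

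**Inputs**

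- Group size: approximately 30 per treatment group (section 2); 20-30 in Table 1.
- Seropositive share p: not given. Assumed 10%, 50% and 90%.
- SD of the log10 fold rise: not given. Assumed 0.3 to 0.5.

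**1. The seropositive MGI alone does not identify the effect.** Take a seropositive MGI of 3, with p = 50% for the last column.

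| MGI, seropositive | MGI, seronegative | True ratio | MGI, all subjects |
|---|---|---|---|
| 3 | 1.5 | 2.0 | 2.12 |
| 3 | 3 | 1.0 | 3.00 |
| 3 | 6 | 0.5 | 4.24 |

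The seropositive-only table shows the same point estimate in all three rows, although the effect runs from a doubling to a halving.

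**2. The MGI for all subjects is a diluted comparator.** On the log scale it is a weighted mean of the strata:

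log MGI(all) = p × log MGI(pos) + (1 − p) × log MGI(neg)

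so that MGI(pos)/MGI(all) = [MGI(pos)/MGI(neg)]^(1 − p).

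For a true ratio of 0.5:

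- p = 10%: 0.5^0.9 = 0.54
- p = 50%: 0.5^0.5 = 0.71
- p = 90%: 0.5^0.1 = 0.93

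Dilution is slight when few subjects are seropositive and severe when most are.

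**3. Back-calculation is possible but not planned.** Rearranging gives

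log MGI(neg) = [log MGI(all) − p × log MGI(pos)] / (1 − p).

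In the last row of the table this is 4.24² / 3 = 5.99, or 6 apart from rounding. It requires p among the same subjects who enter both MGIs, and p below 100%.

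**4. Precision once both strata are tabulated.** With a seropositive and b seronegative subjects in a group of N, the 95% CI multiplies and divides the ratio by

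10^[t(0.975, N − 2) × SD × √(1/a + 1/b)].

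For N = 30, t = 2.048:

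- a = b = 15: √(2/15) = 0.365, giving a factor of 1.68 (SD 0.3) to 2.37 (SD 0.5).
- 3 against 27, either way round: √(1/3 + 1/27) = 0.609, giving 2.37 to 4.20.

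For N = 20, the lower end of Table 1, the same formula gives 1.91 to 2.95 for 10 against 10, and 2.95 to 6.07 for 2 against 18. The ratio can be estimated, but imprecisely where one stratum is small.

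**The case against.** The strongest reply is that the gap is in the wording and does little harm. The objective is tertiary and exploratory, section 6 says "All analyses will be descriptive", and no hypothesis test or primary or secondary result depends on it. The inputs are in the plan, and table layouts sit in TFL annexes that are not at hand and might already hold a seronegative row. All of this bears on severity. It does not remove the mismatch: a descriptive effect still needs both strata, and the SAP text does not ask for the second.

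Several stronger readings are tempting, and the document does not support them:

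- **That the objective cannot be answered, or that seronegative subjects go unreported.** They are included in the MGI for all subjects, and a seronegative point estimate could be back-calculated. If few subjects are seropositive, the all-subject value is a close proxy (0.54 for a true 0.5 at 10%). What is correct is that no planned output answers the objective.
- **That each cohort yields a single figure.** Section 6.2.1 works by study group and section 8 by treatment group, so adjuvanted and unadjuvanted groups are reported separately. Neither has a seronegative comparator.
- **That serostatus is confounded with the starting stalk titre, so a baseline-adjusted model is required.** The SAP says nothing about stalk titres by HI status, and its objective is defined on the unadjusted MGI. An ANCOVA could be added, but it is a preference and would be unstable with very few seropositive subjects.
- **That wide intervals in a small seropositive stratum measure the harm.** They reflect stratum size, which the SAP does not state, and a seronegative column would not narrow them.

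**Conclusion.** The mismatch stands. The plan states an effect as its objective and tabulates only one of the two strata that define it. The omission itself is read directly from sections 3.3, 4.3, 6.2.1 and 6.2.2.1 and rests on no assumption. The size of the dilution does depend on assumed seropositive shares, and the interval factors on an assumed log10 SD of 0.3 to 0.5.

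Severity is minor to moderate. The objective is tertiary and descriptive, the data needed are already planned, and primary and secondary conclusions do not change.

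**What to change.** In sections 6.2.1 and 4.3, for the adult H5N1, H9N2 and H1N1 cohorts and within each treatment group:

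- tabulate the Day 21/Day 0 anti-H1 stalk ELISA MGI with 95% CI, and the number of subjects, for both HI-seropositive and HI-seronegative subjects;
- give the seropositive/seronegative MGI ratio with its 95% CI;
- where a stratum is very small (a threshold set beforehand, for example fewer than 5), list the individual values.

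An analysis adjusted for the Day 0 stalk titre may be added, but is optional.

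The cost is a sentence in section 6.2.1, a matching line in section 4.3, and one more column plus the ratio in the table template. No new samples or assays are needed. The drawback is a wide interval wherever one stratum is small, which the report should say plainly.
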